#### 6.0 Study Objectives and Endpoints

#### 6.1. Objectives

#### 6.1.1 Primary Objective

To assess the efficacy of Bavisant compared to placebo after a 6-week treatment period on the excessive daytime sleepiness in Parkinson's disease.

#### 6.1.2 Secondary Objective(s)

To assess the efficacy and safety assessment of Bavisant compared to placebo after 2 weeks and 6 weeks of treatment. The efficacy assessment will include excessive daytime sleepiness, motor control, and depression.

#### **6.1.3** Exploratory Objective(s)

Exploratory objectives will include the assessment of free living activity in subjects on Bavisant compared to placebo after 6 weeks of treatment using a wrist-worn actigraphy device and pharmacogenomics analysis.

#### 6.2. Endpoints

#### **6.2.1** Primary Endpoint

The primary endpoint will be the mean absolute change of Bavisant treatment groups in the Epworth Sleepiness Scale (ESS) from baseline to the end of the 6-week treatment period, assessed as both the intragroup change compared to baseline and intergroup change compared to placebo.

#### **6.2.2** Secondary Endpoint(s)

Efficacy in Excessive Daytime Sleepiness (EDS):

- Mean absolute change in the Epworth Sleepiness Scale (ESS) from baseline to the end of the 2-week treatment period.
- ESS clinical response, defined as ESS absolute decrease from baseline of at least 3.0 points, after 2 and 6 weeks of treatment.
- ESS clinical response, defined as ESS  $\leq$  10 after 2 and 6 weeks of treatment.
- ESS clinical response, defined as either ESS  $\leq$  10 after 2 and 6 weeks of treatment or ESS absolute decrease from baseline of at least 3.0 points after 2 and 6 weeks of treatment.
- Mean relative change in the Epworth Sleepiness Scale (ESS) from baseline to the end of the 2-week and 6-week treatment periods (percentage of absolute decrease compared to baseline ESS).
- Mean absolute change in the Scales for Outcome in Parkinson's Disease Sleep (SCOPA-Sleep) from baseline to the end of the 2-week and 6-week treatment period.

Amendment 04, Final Version 1.0
Protocol No.: BB-2001-201b
EudraCT No.: 2017-000877-35
Page 37 / 142

• Mean absolute change in the Parkinson's Disease Sleep Scale (PDSS-2) from baseline to the end of the 2-week and 6-week treatment period.

- Mean absolute change in the Maintenance of Wakefulness Test (MWT) from baseline to the end of the 6-week treatment period.
- Mean absolute change in the polysomnography from baseline to the end of the 6-week treatment period.

Efficacy in Parkinson's disease (PD):

- Mean absolute change in the UDPRS scale Part III (motor control) from baseline to the end of the 2-week and 6-week treatment period.
- Mean absolute change in the depression HAM-D score from screening/baseline to the end of the the 2-week and 6-week treatment period and safety follow-up.
- Mean absolute change in the Montreal Cognitive Assessment MoCA score from screening/baseline to the end of the 6-week treatment period.
- Mean absolute change in the Fatigue Severity Scale FSS score from screening/baseline to the end of the 6-week treatment period.

The safety of Bayisant compared to placebo will be assessed by the evaluation of the following:

- Incidence of Adverse Events (AEs), Serious Adverse Events (SAEs), and Adverse Events of Special Interest (AESIs) such as headache, nausea and insomnia
- Incidence of suicidal ideation (C-SSRS) findings from screening/baseline to the end of the 2-week and the 6-week treatment period and safety follow-up
- Incidence of positive psychotic symptoms (BPRS+) findings from screening/baseline to the end of the 2-week and the 6-week treatment period and safety follow-up
- Incidence of physical examination, vital signs and laboratory tests findings (haematology and biochemistry)
- Incidence of cardiovascular safety findings (blood pressure, heart rate, ECG including QT/QTc)
- Incidence of eye exam findings

# **6.2.3** Exploratory Endpoint(s)

The efficacy of Bavisant compared to placebo after the 6-week treatment period of free living activity will be assessed by means of wrist-worn actigraphy. For each set of continuous tri-axial accelerometry measurement, descriptive statistics of values at baseline, endpoint and change from baseline will be provided by treatment group.

A pharmacogenomic analysis will be used to identify genetic reasons why certain people respond differently to Bavisant, to find out more information about how Bavisant works, and to generate information needed for research, development, and regulatory approval of tests to predict response to Bavisant, and to identify variations in genes related to the biological target of Bavisant.

Amendment 04, Final Version 1.0
Protocol No.: BB-2001-201b
EudraCT No.: 2017-000877-35
Amendment 04, Final Version 1.0
07/Nov/2018
Page 38 / 142

### 7.0 Investigational Plan

# 7.1. Overall Study Design and Plan: Description

This phase 2b study is designed as multicentre, multinational, randomized, double blind, parallel group and placebo controlled with three doses of Bavisant (0.5, 1, and 3 mg/d) in subjects with excessive daytime sleepiness with Parkinson's disease. This study will involve approximately 230 subjects from around 48 sites globally.

Eligible subjects will be randomly allocated at a ratio of 1:1:1:1 to either Bavisant (at doses of 0.5, 1, and 3 mg/d) or placebo.

After signing the study informed consent, subjects meeting the UK PDS Brain Banks Diagnostic Criteria for Parkinson's disease (see details in Appendix 18.2) will enter a screening period (lasting up to 3 weeks) followed by a baseline period (lasting up to 1 week). Key inclusion / exclusion criteria will be verified to determine subject eligibility at the screening, baseline periods and prior to randomisation, including the suicide risk assessment following the FDA Guidance for Industry on Suicidal Ideation and Behavior.

[figure not shown]
There is a 6 weeks treatment period, starting on Day 1, followed by a safety follow-up at least 4 weeks after completion of the treatment period. Additional unscheduled visits may be required based on the investigators' judgement at the end of study visit or at the safety follow-up. For early termination, all the assessments of the treatment week 6 visit should be performed, if possible, including the safety follow-up 4 weeks after the last IMP administration.

A schematic of the study design is included in Figure 1 and the schedule of assessments is listed in Appendix 18.15.

Protocol No.: BB-2001-201b 07/Nov/2018 EudraCT No.: 2017-000877-35 Page 39 / 142

Figure 1. Study figure

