#### **Main Criteria for Exclusion:**

- (1) Subjects with excessive daytime sleepiness due to conditions other than Parkinson's disease (including narcolepsy)
- (2) Subjects with significant eye disease which may substantially impact the subject's mobility and ability to have eye examination conducted as per investigator's judgement.
- (3) Subjects with a recent history of suicide attempt (defined as an active, interrupted or aborted attempt within the past 1 year), or reports suicidal ideation in the past 3 months as indicated by a positive response on the C-SSRS at screening visit (an answer of 'yes' to any of the 6 questions)
- (4) Subjects with clinical evidence of depression with significant psychiatric comorbidities (Hamilton Rating Scale for Depression HAM-D score ≥ 17; with or without treatment)
- (5) Subjects with evidence of significant Cognitive Impairment (Montreal Cognitive Assessment MoCA score ≤ 22 at screening)
- (6) Subjects with evidence of significant fatigue (Fatigue Severity Scale FSS  $\geq$  36)
- (7) Subjects with high risk of sleep apnoea (Berlin questionnaire with  $\geq 2$  categories where the score is positive)
- (8) Subjects taking any of the following prohibited medications at screening:
  - Alerting agents, including r-modafinil, modafinil or methylphenidate
  - Benzodiazepines
  - Histamine active agents
  - Hypnotics
  - Cholinergics
  - Skeletal muscle relaxants
  - Clozapine
  - Atomoxetine
  - Amitriptyline
  - Any other daytime medications which affect sleep
- (9) Subjects with chronic oral and / or ophthalmic steroidal use
- (10) Subjects with either renal or hepatic impairment defined by laboratory parameters >1.5x age-adjusted limits of normal range
  - Hepatic damage: Alanine aminotransferase [ALT], aspartate aminotransferase [AST], alkaline phosphatase, or total bilirubin
  - Renal damage: Blood creatinine, blood urea nitrogen [BUN], or estimated glomerular filtration rate [eGFR] < 60 mL/min/1.73m^2

Amendment 04, Final Version 1.0
Protocol No.: BB-2001-201b
EudraCT No.: 2017-000877-35
Amendment 04, Final Version 1.0
07/Nov/2018
Page 23 / 142

- (11) Subjects with abnormal ECG time intervals at baseline including QTc (> 450 for males and > 470 for females)
- (12) Subjects with known history of lung malignancy.
- (13) Subjects with known history of abuse of alcohol or other addictive substances in the 6 months prior to inclusion.

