(EDS) (Epworth Sleepiness Score [ESS] > 12 at screening). Stable medication for at least 4 weeks before screening is mandatory regarding medication which may affect sleep (for example, dopaminergics, L-dopa, monoamine oxidase inhibitors, antipsychotics, or hypnotics). The exclusion criteria will exclude subjects with EDS due to conditions other than Parkinson's disease (including narcolepsy and sleep apnoea), any significant eye disease which may have an impact on a subject's mobility (which could hamper the study assessments), clinical evidence of depression (HAM-D score ≥ 17, as a certain degree of depression is shown by most of the PD subjects), positive response on the C-SSRS (an answer of 'yes' to any of the 6 questions), clinical evidence of cognitive impairment (MoCA score  $\leq 22$ , as it could interfere with the study assessments), clinical evidence of fatigue (FSS  $\geq$  36, for similar reasons), any alerting medication (including r-modafinil, modafinil or methylphenidate), benzodiazepines, histamine active agents, clozapine, atomoxetine, skeletal muscle relaxants, or any other daytime medications which affect sleep (in order to avoid any selection bias). Subjects with hepatic, renal, cardiac (ECG, including QTc), or ophthalmological impairment will not be entered into the study. The suicide risk will be assessed (C-SSRS) before and after treatment administration at all study visits including followup following the the FDA Guidance for Industry on Suicidal Ideation and Behavior. BPRS+ (Brief Psychiatric Rating Scale) positive subscale to monitor psychotic symptoms and HAM-D to monitor depression will be assessed at all study visits (including follow-up). These assessments are included because patients with Parkinson's disease are known to be at higher risk of psychosis and depression than the general population. Follow-up procedures for a positive finding on the C-SSRS, or an elevated HAM-D or psychosis scale score will be managed as per the standard of care at the site, including an assessment by the investigator of the need for further mental health evaluation. Vital signs (including blood pressure and heart rate) will be assessed at all study visits (including follow-up) as patients with Parkinson's disease are known to commonly exhibit orthostatis and other cardiovascular changes.

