## 8.4.1.15.4 Columbia-Suicide Severity Rating Scale (C-SSRS)

The Columbia-Suicide Severity Rating Scale (C-SSRS) will be assessed at screening, visit 2 (day 14), visit 3 (day 42) or early termination, and follow-up visit (28 days after the last IMP administration).

The C-SSRS supports suicide risk assessment through a series of simple, plain-language questions that anyone can ask. The answers help users identify whether someone is at risk for suicide, assess the severity and immediacy of that risk, and gauge the level of support that the person needs. Users of the C-SSRS tool ask people whether and when they have thought about suicide (ideation), what actions they have taken (and when) to prepare for suicide, and whether and when they attempted suicide or began a suicide attempt that was either interrupted by another person or stopped of their own volition.

Columbia University, the University of Pennsylvania, and the University of Pittsburgh — supported by the National Institute of Mental Health (NIMH) — developed the screening tool for a 2007 NIMH study of treatments to decrease suicide risk among adolescents with depression. The C-SSRS, based on more than 20 years of scientific study, filled an urgent need for suicide research and prevention: a better way to uniformly and reliably identify people who are at risk. The C-SSRS achieved accurate and comparable results by using consistent, well-defined, and science-based terminology. Just as important as its ability to identify who might attempt suicide, it was the first scale to assess the full range of a person's suicidal ideation and behavior, including intensity, frequency, and changes over time.

In 2011, the Centers for Disease Control and Prevention adopted the scale's definitions for suicidal behavior and recommended the use of the C-SSRS for data collection. In 2012, the Food and Drug Administration declared the C-SSRS the standard for measuring suicidal ideation and

Protocol No.: BB-2001-201b EudraCT No.: 2017-000877-35 Amendment 04, Final Version 1.0 07/Nov/2018 Page 56 / 142

behavior in clinical trials. Today, the C-SSRS is used in clinical trials, public settings, and everyday situations, such as in schools, faith communities, hospitals, and the military, to identify who needs help — saving lives in 45 nations on six continents.

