### 8.4.2 Study Procedures

# Screening assessments (Day -28 to Day -8)

Subjects will be screened for enrolment within 3 weeks prior to the start of baseline assessments. Subjects will be screened in accordance with predefined entrance criteria as described in Sections 8.1 and 8.2. See Section 8.5.1 for the procedure for documenting screen failures.

Procedures to be completed at screening include:

- Subject information/Informed consent signed and dated.
- Assessment of inclusion / exclusion criteria.
- Demographics
- Medical history and previous medication (prohibited as of 4 weeks before D-28)
- Concurrent medical condition
- Physical examination
- Vital signs

Amendment 04, Final Version 1.0
Protocol No.: BB-2001-201b
EudraCT No.: 2017-000877-35
Page 59 / 142

- For women of childbearing potential the method of contraception must be documented (as CM as applicable)
- Laboratory (haematology, biochemistry), serum pregnancy test (for women of childbearing potential)
- Pharmacogenomic blood sample
- Electrocardiogram, heart rate, blood pressure
- Eye examination
- Cognitive assessment (MoCA)
- Columbia-Suicide Severity Rating Scale (C-SSRS)
- Fatigue assessment (FSS)
- Assessment of sleepiness scales: ESS
- Other scales: HAM-D, BPRS+ and Berlin Questionnaire
- Determination of subject eligibility
- Recording of adverse events

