# Randomisation Visit 1 (Day -1)

- Re-assessment of inclusion / exclusion criteria.
- Urine dipstick for pregnancy assessment.
- Assessment of sleepiness scales: ESS, SCOPA-Sleep, PDSS-2
- Other scales: UPDRS Part III
- Wrist-worn actigraphy (GENEActiv®) assessment 7 days continuously before the first dose on Day 1
- Vital signs (including heart rate and blood pressure)
- Confirmation of subject eligibility
- Subjects will be randomised to their treatment assignments
- Study drug dispensing
- Recording of adverse events
- Recording of concomitant medication

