# Treatment Visit 2 (Day 14 ±2)

This visit will be performed 2 weeks after the 1st treatment administration (Day 1). The following examinations/procedures will be performed:

- Vital signs (including heart rate and blood pressure)
- Assessment of sleepiness scales: ESS, SCOPA-Sleep, PDSS-2
- Other scales: UPDRS Part III, C-SSRS, HAM-D, BPRS+
- Dispensing of double blind study medication
- Drug return and accountability
- Recording of adverse events
- Recording of concomitant medication

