### 8.6.3 Dosages and Regimen

Each subject who qualifies for the study will receive wallet cards containing tablets of double-blind study medication. Subjects will receive 1 wallet card of their assigned treatment at Visit 1 (for 2 weeks treatment period) and 2 wallet cards at Visit 2 (for 4 weeks treatment period).

Subjects will be instructed to take 1 tablet orally per day at the same time in the morning, with or without food. The first dose is to be taken the day after randomisation when study medication has been dispensed to the subject.

The investigator or designee must instruct the subject to bring each of their study medication containers (wallet cards) to each clinic visit, regardless of whether the study medication cards are empty.

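### No C-SSRS is scheduled between screening and randomisation, although Protocol 7.1 and 7.2 imply a check at that point; separately, the sections disagree on vital signs at Visit 1

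*Protocol*

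**What the plan says.** **Suicide risk, general statements.** Protocol 7.1 has key criteria verified for "eligibility at the screening, baseline periods and prior to randomisation, including the suicide risk assessment". Protocol 7.2 adds: "The suicide risk will be assessed (C-SSRS) before and after treatment administration at all study visits", with follow-up included. Section 8.4 names the study visits, and Randomisation Visit 1 on Day -1 is among them.

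**Suicide risk, operational text.** Section 8.4.1.15.4 says the scale "will be assessed at screening, visit 2 (day 14), visit 3 (day 42) or early termination, and follow-up visit". The 8.4.2 lists and the C-SSRS row of 18.15 agree with it: the scale appears at screening, and is absent from the baseline period and Visit 1. The ideation part of exclusion 3 (Summary and 8.2) rests on a "positive response on the C-SSRS at screening visit". Both the baseline and Visit 1 lists contain a general re-assessment of the inclusion and exclusion criteria, and footnote 3 of 18.15 repeats this.

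**Vital signs.** The Visit 1 list in 8.4.2 includes vital signs with heart rate and blood pressure. Section 8.4.1.7 names screening, Visit 2, Visit 3 or early termination, and follow-up, without Visit 1. The vital-signs row of 18.15 has no entry at Visit 1 either. SAP 12 takes the last value before the first dose as the safety baseline.

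**The concern.** The general sections describe a suicide-risk check close to randomisation; the sections that sites work from do not schedule one. Re-assessing exclusion 3 on Day -1 can be done by re-reading the screening answer, because the criterion itself points there. A subject who develops ideation after screening and does not volunteer it could then be randomised without the structured questions being asked again.

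Nothing else scheduled on Day -1 fills the gap. HAM-D, which has a suicide item, is not given at Visit 1, and the only clinician-rated scale there is UPDRS Part III, a motor examination.

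For vital signs, the stake is the baseline behind the safety change flags. Its age depends on which section a site follows, and it could differ between sites.

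**Working it through.** No sample-size, power or alpha figure is involved. The check is day arithmetic on the visit windows plus a comparison of the sections.

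**Inputs**
- Screening: Day -28 to Day -8 (8.4.2, 18.15).
- Randomisation: Day -1 (8.4.2, 18.15).
- First dose: Day 1. Section 8.6.3 states "The first dose is to be taken the day after randomisation", so there is no Day 0 and Day -1 to Day 1 counts as one day.
- Visit 2: Day 14 ±2, that is Day 12 to Day 16. Visit 3: Day 42 ±3, that is Day 39 to Day 45.

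**Age of the last C-SSRS**
- At randomisation: -1 - (-28) = 27 days at most; -1 - (-8) = 7 days at least.
- At first dose: 27 + 1 = 28 and 7 + 1 = 8 days.
- With a rating at Visit 1 these ages become 0 and 1 day.

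**Gap between consecutive scheduled ratings**
- Day 1 to Day 12 is 11 days; Day 1 to Day 16 is 15 days.
- Screening to Visit 2: shortest 7 + 1 + 11 = 19 days; longest 27 + 1 + 15 = 43 days.
- Visit 1 to Visit 2, if a rating were added: 1 + 11 = 12 to 1 + 15 = 16 days.
- For comparison, Visit 2 to Visit 3 as planned: 39 - 16 = 23 to 45 - 12 = 33 days.

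**What is repeated before dosing**
- ESS is repeated on Day -1.
- Pregnancy is re-tested by dipstick on Day -1.
- Laboratory tests are repeated in the baseline period if more than 14 days have passed since screening.
- The C-SSRS has no repeat and no maximum age.

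**Vital-signs baseline under SAP 12**
- If 8.4.2 is followed, the baseline is Day -1, 1 day before first dose.
- If 8.4.1.7 or 18.15 is followed, the baseline is screening, 8 to 28 days before first dose.
- SAP 12.6 has four criteria each for systolic pressure, diastolic pressure and heart rate: 3 × 4 = 12. In each set two are changes from baseline (20 mmHg, 10 mmHg and 20 bpm, up and down): 3 × 2 = 6. The other 6 are absolute and unaffected.
- SAP 12.4 also uses baseline for weight change above 5% and for the shift from normal to abnormal respiratory rate.

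**The case against.** The best defence is that 7.1 promises verification of criteria rather than a new rating. The criteria are re-assessed at baseline and Visit 1, and the ideation criterion is by its own terms a screening result. On that reading the operational sections are coherent. MoCA, FSS, HAM-D, the Berlin Questionnaire, ECG and eye examination are likewise done once before dosing, so a single screening rating fits the design's pattern. An age of 7 to 27 days is also not out of line with the planned 23 to 33 days between Visits 2 and 3.

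Much of this stands. A reader might infer that 7.1 by itself requires a second C-SSRS; its wording does not go that far. The phrase about all study visits is also used loosely elsewhere: 8.4.1.7 follows it with a list that omits Visit 1, and 8.4.1.14.1 follows it with a list that includes Day -1 but omits follow-up. The 27-day and 43-day figures are window extremes. The guide in Appendix 18.12 allows for pre-treatment ratings that cover the period since the last visit, but calls itself a general guideline, so it permits a second rating without requiring one.

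The defence does not answer 7.2 read with 8.4, which together put a C-SSRS at Visit 1. Nor can re-reading an earlier answer detect ideation that began afterwards.

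On vital signs, the SAP definition works whichever listing is followed; only the age of the value changes. That makes the point minor, but the sections still conflict.

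**Conclusion.** Both points hold, at modest size.

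- **C-SSRS.** Ideation arising in the 7 to 27 days between screening and randomisation is not actively asked about before the subject is randomised, while 7.2 with 8.4 indicates that it would be. Adding the rating is a cheap improvement that should be made.
- **Vital signs.** The protocol is wrong as written, in a minor way. The baseline for 6 of the 12 blood-pressure and heart-rate criteria, the weight flag and the respiratory-rate shift is either 1 day or 8 to 28 days old at first dose.

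The day counts assume visits within their windows and no Day 0. The documents do not show how often ideation would emerge in the interval or which section sites follow.

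A reader might infer three stronger conclusions that the documents do not support:
- That subjects with new ideation would necessarily be randomised. An investigator may act on clinical evidence, and the suicide-attempt part of exclusion 3 is not tied to the scale.
- That the safety comparison is biased. Both gaps apply before or at randomisation and to all arms, the safety analysis is descriptive, and power is unaffected.
- That HAM-D and BPRS+ must also be given at Visit 1, since 7.2 uses the same phrase for them. Section 7.1 singles out suicide risk, and the loose phrase in 7.2 is too weak alone to require them. Under SAP 9, a HAM-D at Visit 1 taken before randomisation would also move the baseline of that secondary endpoint.

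**What to change.** 1. Add the C-SSRS at Visit 1, before randomisation, in 8.4.1.15.4, 8.4.2 and 18.15. Reword exclusion 3 in the Summary and 8.2 so that the ideation part refers to the C-SSRS at screening or Visit 1. Day -1 closes the baseline period, so one rating serves both the baseline and the pre-randomisation check in 7.1. The exclusion sentence at the end of 8.4.1.15.4 names no visit and needs no change.
2. Add Visit 1 to the vital-signs text in 8.4.1.7 and to the vital-signs row of 18.15, in line with 8.4.2.

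**Cost.** A protocol amendment to these sections. One extra C-SSRS per subject, about 230 for the planned 230 randomised, at an existing visit and by raters the sites already need for screening and Visit 2. The documents give no administration time. A few subjects may be excluded on Day -1. Vital signs need no measurement beyond what 8.4.2 already lists. SAP 12.2 tabulates the C-SSRS at Visit 2, Visit 3 and overall during follow-up, so no SAP table has to change.
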